### **4. Trial population**

#### **4.1. Screening data**

All screening data will be reported in the form of a table (see appendix) containing the numbers and proportions within each category.

#### **4.2. Eligibility**

Eligible participants are people with dementia, over the age of 50 and currently residing within their own home, on the Primary Care Quality Outcomes Framework (QOF) Dementia register who have sustained at least one fall within six months prior to identification as a study participant.

Eligible carers are either a close family member or friend who receive no financial compensation for the care they provide to the patient participant.

#### **4.3. Participant Flow**

Participant flow including recruitment, consent and withdrawal in the Maintain trial will be described through use of a CONSORT diagram.

Numbers of participants declined to consent and withdrawn/lost to follow-up will be included within this CONSORT alongside accompanying reasons.

Withdrawals may either be a partial withdrawal (where a participant withdraws from the intervention but continues to provide data) or a full withdrawal. In both cases, the numbers of partial withdrawals and full withdrawals will be reported.

#### **4.4. Baseline patient characteristics**

The following characteristics will be reported in a table containing both number and proportion reported by group allocation.

For Patients and Carers:

- Age
- Ethnicity
- Sex

For Patients Only:

- Residence Type
- Living Arrangement
- English Language Status
- Education Level
- Smoking Status
- Number of Falls

For Carers Only:

- Frequency of Visits to Patient
- Relationship to Patient

### **5. Statistical Analysis**

#### **5.1. Outcome definitions**

Feasibility Outcomes that will determine whether to proceed to full trial are as follows:

- Proportion of eligible patients consenting to pilot trial
- Proportion of participants that attend  $\geq 60\%$  of sessions as planned
- Proportion of consented participants that provide key outcome data at week 28

Pilot Randomised Controlled Outcomes are as follows:

- Activities of daily living (ADL) assessed with the Disability Assessment for Dementia (DAD) at Baseline and 28 Weeks
- European Quality of Life Instrument (EQ-5D-5L) at Baseline and 28 Weeks
- Quality of Life - Alzheimer's Disease (QOL-AD) at Baseline and 28 Weeks
- International short form Falls Efficiency Scale (Short-FES-I) at Baseline and 28 Weeks
- Timed Up and Go test at Baseline and 28 Weeks
- Goal Attainment Scaling (GAS) (intervention only) at Baseline, 12 Weeks and 28 Weeks
- Cognition assessed with Mini-ACE at Baseline
- Falls Diary assessed during the 6 months of follow up
- Carer burden assessed with the Zarit burden interview 12 (ZBI-12) at Baseline and 28 Weeks
- Carer participant quality of life assessed with the European Quality of Life Instrument (EQ-5D-5L) at Baseline and 28 Weeks
- Carer rated Patient participant quality of life assessed with the EQ-5D-5L proxy at Baseline and 28 Weeks
- Carer rated patient participant quality of life QoL-AD Proxy at Baseline and 28 Weeks
- Health and social care Utilisation Questionnaire (HUQ) at Baseline, 12 Weeks and 28 Weeks

Methods of calculation for all outcomes are defined within the protocol in Table 2.

## 5.2. Analysis Methods

Participant flow through the trial will be summarised using a CONSORT flow diagram for cluster randomised controlled trials.

Baseline characteristics of the services and participants will be described using means and standard deviations for continuous and count variables and numbers and percentages for categorical variables. We will report the following parameters with 95% confidence intervals that are widened to allow for clustering: % of screened people that are eligible; % of eligible people that consent to participate; % of participants that provide data at the 6-month follow-up; and % of intervention arm participants that attend at least 60% of scheduled sessions. To estimate these parameters, mixed logistic regression models with Satterthwaite's degrees of freedom correction will be fitted to binary outcomes that represent eligibility status, consent status, follow-up status and whether attended at least 60% of the scheduled sessions. The constant from these models is the log odds of the parameters which will (along with the 95% CIs) be converted to the percentage scale.

We will also report estimates of the standard deviations for continuous outcomes measured at baseline and week 28.

In order to assess the extent to which randomisation of clusters before recruiting participants may have resulted in recruitment bias due to the research nurses being unblinded, we will report the percentage of eligible people that participate in each of the intervention and control arms and examine the characteristics of the participants between the trial arms.

Finally, in ancillary analyses, we will report intention-to-treat estimates of the effect of the intervention at week 28, using 95% confidence intervals to quantify potential effectiveness. The comparison between trial arms will be undertaken by fitting mixed ("multilevel") linear regression models for continuous outcomes and mixed Poisson regression models for count outcomes; in both instances, using Satterthwaite's degrees of freedom correction to recognise the small number of clusters in the study. Comparisons will be adjusted for the baseline score of the outcome. No p-values will be reported as it is not an objective of this study to conduct a definitive test of the intervention effect.

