#### Definite Go ('green light'):

- ≥ 40% of eligible patients consenting to pilot trial
- ≥ 80% participants attend ≥ 60% of sessions as planned
- Retention of ≥ 70% of consented participants for key outcome data at 6 months
- An indication from qualitative work that the intervention is perceived as acceptable to both participants and professionals.

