### 9.2. Statistical analysis

Analyses will be fully pre-specified in a statistical analysis plan that is signed off by the Trial Steering Committee and the Trial Management Group.

Participant flow through the trial will be summarised using a CONSORT flow diagram for cluster randomised controlled trials.

Baseline characteristics of the services and participants will be described using means and standard deviations for continuous variables and numbers and percentages for categorical variables. We will report the following parameters with 95% confidence intervals that are widened to allow for clustering: % of screened people that are eligible; % of eligible people that consent to participate; % of participants that provide data at the 6-month follow-up; and % of intervention arm participants that attend at least 60% of

Page 45 of 59

scheduled sessions. To estimate these parameters, mixed logistic regression models with Satterthwaite's degrees of freedom correction will be fitted to binary outcomes that represent eligibility status, consent status, follow-up status and whether attended at least 60% of the scheduled sessions. The constant from these models will represent the log odds of the parameters which will (along with the 95% CIs) be converted to the percentage scale.

We will also report estimates of the standard deviations for continuous outcomes measured at baseline, 3 months and 6 months.

In order to assess the extent to which randomisation of clusters before recruiting participants may have resulted in recruitment bias due to the research nurses being unblinded, we will report the percentage of eligible people that participate in each of the intervention and control arms and examine the characteristics of the participants between the trial arms.

Finally, in ancillary analyses, we will report intention-to-treat estimates of the effect of the intervention on the continuous outcomes at 3 and 6 months, using 95% confidence intervals to quantify potential effectiveness. The comparison between trial arms will be undertaken by fitting mixed ("multilevel") linear regression models using Satterthwaite's degrees of freedom correction to recognise the small number of clusters in the study. Comparisons will be adjusted for the baseline score of the outcome. No p-values will be reported as it is not an objective of this study to conduct a definitive test of the intervention effect. Analyses will be undertaken using Stata software.

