**Table 2- Patient Demographics 2**

Patient Demographics	Control Group			Maintain Group		
	N	Mean	SD	N	Mean	S.D
Age						
Number of Falls in the last 6 Months						

Table 3- Carer Demographics 1

Carer Demographics	Control Group			Maintain Group		
	N	Mean	SD	N	Mean	S.D
Age						

Table 4- Carer Demographics 2

Carer Demographics	Control Group		Maintain Group	
	N	n (%)	N	n (%)
How Often does Carer Typically See Patient				
Every Day				
Most Days				
Once a Week				
Less than Once a Week				
Relationship to Patient				
Spouse/Partner				
Son/Daughter				
Grandchild				
Sibling				
Other Family Member				
Friend				
Other				
Ethnicity				
White				
Mixed/Multiple Ethnic Groups				
Asian/Asian British				
Black/African/Caribbean/Black British				
Other				
Sex				
Male				
Female				

Table 5- Stop/Go Criteria Outcomes

Screening/Eligibility Feasibility Outcomes	N	n (%)
Proportion of Eligible Patients Consenting to Pilot Trial		

Proportion of Participants who Attend <math>\geq 60\%</math> of Sessions as Planned.		
Proportion of consented participants retained for key outcome data at week 28		

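### The mixed-logistic constant is not the percentage of people that the progression criteria use, and the plan does not say which of its two percentages is judged

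*SAP*

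**What the plan says.** Protocol 4.4 sets the green thresholds as percentages of people: "≥ 40% of eligible patients consenting to pilot trial", "≥ 80% participants attend ≥ 60% of sessions as planned" and "Retention of ≥ 70% of consented participants for key outcome data at 6 months". SAP 5.1 lists the same three quantities as the outcomes that decide progression, for example "Proportion of eligible patients consenting to pilot trial".

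SAP 5.2 says how they are estimated: "mixed logistic regression models with Satterthwaite's degrees of freedom correction will be fitted to binary outcomes". It then says "The constant from these models is the log odds of the parameters", and that the constant and its 95% interval are converted to percentages. Protocol 9.2 has "The constant from these models will represent the log odds of the parameters". Both sections say that the intervals will be widened for clustering.

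SAP Table 5, the stop/go table, has a row "Proportion of Eligible Patients Consenting to Pilot Trial" and matching rows for attendance and retention. Its columns are N and n (%), which is the raw percentage. It has no interval column and no model-based figure.

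**The concern.** In a random-intercept logistic model the constant describes a site with random effect zero, that is, the median site. The percentage of people is an average over all sites. On the logistic scale the two agree only if sites do not differ or the rate is 50%. Otherwise the constant lies further from 50% than the average does, so the sentence in SAP 5.2 is false for the parameters it names.

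These percentages are the main output of a pilot trial. The plan yields a raw n/N in Table 5 and a model figure from 5.2, and neither document says which is compared with 40%, 80% or 70%. If they fall on opposite sides of a threshold, the choice would be made after seeing the data. The interval also depends on a between-site variance estimated from three sites (attendance) or six (consent and retention), which is very little information.

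**Working it through.** **Inputs.** From protocol 9.1 and SAP 2.3: six sites, three per arm, 10 participants each; 150 eligible people (25 per site if equal) with 40% consenting; ICC 0.05. Thresholds are from protocol 4.4. Site counts in the examples are assumed.

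**1. The plan's own intervals.** The design effect is 1 + (m − 1) × 0.05. This is 2.20 for m = 25 and 1.45 for m = 10. Effective sample sizes are 150/2.20 = 68.2, 60/1.45 = 41.4 and 30/1.45 = 20.7. Jeffreys intervals on these give:

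| Parameter | Recomputed | Plan |
|---|---|---|
| Consent, 40% of 150 | 29.0 to 51.8% | 29 to 51% |
| Retention, 80% of 60 | 66.0 to 89.9% | 66 to 91% |
| Attendance, 80% of 30 | 59.6 to 92.7% | 60 to 93% |

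All limits agree within about 1.1 points. The sample size section therefore already uses an interval of roughly this kind, with a fixed ICC.

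**2. Constant against population percentage.** With site effect u ~ N(0, s²), the population percentage is the average of expit(b + u), and the plan reports expit(b). The ICC of 0.05 can be read in two ways:

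- Latent scale: s² = (0.05/0.95) × π²/3 = 0.173.
- Proportion scale: s² such that the variance of site rates is 0.05 × p(1 − p). This gives 0.23 at 40% and 0.33 at 80%.

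| True percentage | expit(b), latent | expit(b), proportion |
|---|---|---|
| 80% | 80.8% | 81.5% |
| 70% | 70.7% | 71.0% |
| 40% | 39.6% | 39.5% |

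The constant overstates attendance and retention and, with similar-sized sites, understates consent. If the ICC were 0.20 (assumed), 80% would become 83.3 to 85.8%.

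**3. Example data.** Maximum-likelihood random-intercept fits:

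| Counts by site | Raw n/N | Constant |
|---|---|---|
| Attendance 5, 8, 10 of 10 | 23/30 = 76.7% (amber) | 82.1% (green) |
| Retention 9, 9, 8, 7, 5, 3 of 10 | 41/60 = 68.3% (amber) | 70.8% (green) |
| Consent 16, 13, 11, 9, 7, 4 of 25 | 60/150 = 40.0% (green) | 39.3% (amber) |
| Consent, 10 each from 13, 16, 20, 25, 40, 50 | 60/164 = 36.6% (amber) | 42.7% (green) |

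The last row has a different cause: site weighting. Site weights are roughly 1/(s² + 1/(n p(1 − p))). The fitted s is 0.75, so s² = 0.56. With p = 0.4, the sites with 13 and 50 people get 1/(0.56 + 0.32) = 1.1 and 1/(0.56 + 0.08) = 1.6, although one is nearly four times the size of the other. If sites with more eligible people consent at lower rates, the constant overstates consent. Integrating out the random effect does not repair this: it gives 43.5%.

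**4. How often a threshold is crossed.** In beta-binomial simulations with the true rate at the threshold and ICC 0.05, amber became green in 2.2 to 2.7% of runs for attendance and 1.7 to 3.8% for retention (two sets, 400 to 1,000 runs per setting). For consent with equal sites, no run went amber to green and 3.8% went green to amber. With 10 to 45 eligible people per site (assumed), the figures were 1.8% and 5.2%. At an assumed ICC of 0.15, amber to green rose to 5.4% for attendance and 7.2% for retention.

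**5. Variance estimated as zero.** With three sites of 10, the variance estimate is zero when Σ(xᵢ − 10p)² ≤ 30p(1 − p), where p = n/N. For 6, 8 and 9 of 10, p = 0.767: the left side is 2.78 + 0.11 + 1.78 = 4.67 and the right side is 5.37, so the estimate is zero. At p = 0.8 and ICC 0.05 this occurs in about 63% of simulated data sets. The standard error is then the simple binomial one. The SAP does not say how a Satterthwaite correction would be applied to a logistic fit; any such correction would change only the multiplier.

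**The case against.** The strongest reply is that nothing says the constant is the decision figure. The criteria are worded as percentages of people, and the only stop/go table shows raw n (%). A reader might infer that the plan will judge progression on a biased number; the documents do not support that. They support the narrower statement that two figures exist and no rule chooses between them. Nor is the decision mechanical: protocol 4.4 adds a qualitative criterion, sends amber results to refinement, and leaves progression to discussion by the Trial Steering Committee.

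The size is also modest. The average shift at the planned ICC is about 0.4 to 1.5 points, against a planned attendance interval of 60 to 93%. When the variance is estimated as zero, the constant equals n/N exactly, so the shift and the missing widening mostly do not occur together. All of this stands.

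Two other tempting readings fail. One is that the constant generally inflates consent: with similar-sized sites it deflates it, and only a link between site size and consent rate reverses that. The other is that near-100% constants from patterns such as 3, 10, 10 of 10 measure the bias: the variance estimate diverges there, so they show instability only.

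The reply does not rescue the sentence itself. SAP 5.2 names the model as the way to estimate these parameters, and what it says of the constant is untrue when sites differ.

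**Conclusion.** The point holds as a should-fix. SAP 5.2 and protocol 9.2 misdescribe the constant, the plan gives two percentages per criterion with no rule for which is judged, and with three sites the interval will often not be widened for clustering.

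The expected distortion at ICC 0.05 is about 1 point upward for attendance and retention and about half a point downward for consent with similar-sized sites. Threshold crossings are uncommon, at about 2 to 4% of runs even with the true rate at the threshold. They become more frequent if sites differ more than planned. These figures assume normal random effects for the average shift, beta-binomial site variation for the simulations, and 10 participants or 25 eligible people per site unless stated. The site counts are illustrations, not forecasts.

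**What to change.** - In SAP 5.2 and protocol 9.2, define each parameter as n/N over all relevant people, and state that this figure is compared with the thresholds in protocol 4.4.
- Give n/N a 95% interval that does not rest on a variance estimated from three to six sites. One option is a design-effect interval with the pre-stated ICC of 0.05, as in the sample size section, with a larger ICC as a check. For attendance at 80% of 30 and an assumed ICC of 0.15, the design effect is 1 + 9 × 0.15 = 2.35, the effective sample size is 30/2.35 = 12.8, and the Jeffreys interval is about 53 to 95%.
- Add the interval and site-level n/N to SAP Table 5.
- Delete the sentence about the constant, or keep the constant labelled as a typical-site rate.

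This costs a few lines of text and simpler code, and needs no new data. The intervals may be wider than the model's, and they depend on an assumed ICC, which is why the larger value should be shown beside them.

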#### 7.7. Follow up Assessments

The clinical researcher will carry out a second visit to repeat most of the outcome measures completed at baseline with the PWD and their informal carer (see Table 2). For those in the intervention arm, this will take place 26 weeks after the start of the intervention. For those in the control arm, this will take place 28 weeks from baseline. The HUQ will also be completed at three months follow up by phone call. A fidelity checklist will be used to measure intervention fidelity.

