#### 7.8. Quantitative assessment of falls

PWD will be asked to complete a prospective falls diary for the duration of the six month follow up period with the aid of an unpaid carer if required. These will be used to calculate:

Page 36 of 59

- the fall rate per person per year
- the proportion of participants with one or more falls
- injury and fracture rates

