# 10. Data management

#### 10.1. Data collection tools and source document identification

Data will be handled, computerised and stored in accordance with the Data Protection Act 2018. Patients' will be given a copy of their signed consent form to keep, a copy will be filed in the patients' medical notes and a copy will be filed in the investigator site file. A scanned copy will be uploaded to the secure online EDC system by site staff, in which only authorised members of the trial team will be able to access. The consent forms will be checked by an authorised member of the trial team and then deleted after the check is complete.

Paper case report forms (CRFs) designed by Exeter Clinical Trials Unit will be used to collect data which will then be input into a secure online study EDC system. CRFs will capture the date of completion and name of the person completing the CRF. The EDC system will mirror the paper CRFs and will be able to audit the users entering data, amending data and any other data changes. The eCRFs will be validated to query discrepancies in the data as well as querying missing data. SAE data will be the only exception to this method and will be entered into the EDC system directly (medical records will be used for source data). Audio recordings from qualitative interviews will be transcribed and the transcriptions will be saved as source data.

When data are captured on a CRF as the first recording of the data (e.g. participant reported outcome measures), the CRFs are the source data. Where data are accessed from medical records, the medical records will be the source data. Data on standardised outcome measures will be collected on the CRFs by clinical researchers. Data for the health economics component (HUQ) will be integrated into the CRFs. CRFs will be pseudonymised to protect the identity of the participants. Paper CRFs completed at the 6-month visits in participants' homes will be transferred to the participating site by the research nurse (or equivalent) where the data will be transcribed into the EDC system. Paper intervention CRFs will be stored securely at the relevant Trust premises and posted to Exeter CTU at the end of the intervention period. Data will then be entered into the EDC by an authorised member of the research team. Diaries will be returned to the research team at the end of the intervention. Data from the diaries will also be entered on to the EDC system.

Page 48 of 59

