**Table 16- Frequency of Falls Assessed Using the Falls Diary**

Patient Health Related Quality of Life Outcomes	Maintain Group			Control Group			Model Statistics	
	N	Mean	SD	N	Mean	SD	IRR	95% CI
Falls Diary at 28 Weeks								

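### The falls model and its results table leave out person-time and participant-level overdispersion, although the protocol defines the outcome as a rate per person-year

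*SAP*

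**What the plan says.** SAP 5.2 specifies "mixed Poisson regression models for count outcomes", "using Satterthwaite's degrees of freedom correction to recognise the small number of clusters in the study", and adds "Comparisons will be adjusted for the baseline score of the outcome". It names no exposure term, random-effect structure or dispersion term. SAP 5.5 plans no sensitivity analysis. In SAP Table 16 the single row, "Falls Diary at 28 Weeks", has columns for N, mean, SD, IRR and 95% CI, and none for person-time.

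Protocol 7.8 derives three results from the diary: "the fall rate per person per year", the proportion who fall at least once, and injury and fracture rates. The SAP has no analysis or table for the second and third. On derivations SAP 5.1 says: "Methods of calculation for all outcomes are defined within the protocol in Table 2". That table also defines falls as an annual rate per person.

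On timing, protocol 7.7 states: "For those in the intervention arm, this will take place 26 weeks after the start of the intervention". It puts the control visit 28 weeks from baseline. SAP 2.7 gives 26 weeks to control and 28 to intervention. Both protocol Table 2 and 7.8 describe a six-month diary, but neither gives a start date. Protocol Table 3 marks the diary under Week 1 and Weeks 2–28 only. Protocol 10.1 says: "Diaries will be returned to the research team at the end of the intervention".

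**The concern.** A Poisson model without an offset compares mean counts per participant. That is a rate ratio only if both arms are observed for the same average time. Here observation time is not controlled. Protocol 7.10 expects some participants to become ill or die, the sample size section uses 80% follow-up, SAP 2.7 keeps out-of-window data, and no rule says how a part-completed diary is counted.

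Falls in people who have already fallen are also likely to vary between individuals by more than a Poisson distribution allows. A model whose only random effect is the site has no place for that variation except the site term.

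Finally, a prospective diary has no baseline score, so the stated adjustment has nothing to act on as written. SAP Table 2 does tabulate falls in the last six months, but the SAP does not name them as the covariate.

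At stake is whether the falls estimate carried into planning of the main trial is the rate ratio that the protocol promises, with an interval that can be trusted.

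**Working it through.** **Inputs from the documents.** Six clusters, three per arm, 60 participants and 80% follow-up (SAP 2.3), so 60 × 0.80 / 6 = 8 per cluster and 24 per arm. Visits at 26 and 28 weeks (protocol 7.7; reversed in SAP 2.7), with a two-week window (SAP 2.7). The first intervention assessment is arranged within two weeks of baseline (protocol 7.6). The documents give no fall rate, dispersion or person-time, so there is no falls figure of the plan's own to reproduce.

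**Step 1, exposure.** Without an offset, estimated IRR = true IRR × (mean diary time, intervention ÷ mean diary time, control). With true IRR = 1:

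| Reading | Weeks, intervention v control | Null IRR |
|---|---|---|
| Protocol 7.7, diary from intervention start v from baseline | 26 v 28 | 0.93 |
| Protocol 7.7, diary from baseline in both arms | 26–28 v 28 | 0.93–1.00 |
| SAP 2.7 | 28 v 26 | 1.08 |
| Equal diary time | – | 1.00 |
| Opposite window edges, protocol timing | 24 v 30 | 0.80 |
| Opposite window edges, SAP timing | 30 v 24 | 1.25 |

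The last two rows are outer limits, since every visit in an arm would have to fall at the edge of its window.

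A simulated case assumed a mean of 2 falls, k = 1, site SD 0.2, and 26 v 28 weeks. It gave an IRR of 0.92 without an offset and 0.995 with one. The t(4) coverage was 93.6% and 94.3%. The interval spanned a factor of about 2.4 each way, so a 7% shift barely moves coverage.

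**Step 2, overdispersion (assumed).** Let counts have variance/mean = 1 + kμ, with mean μ and dispersion k. With n = 24 per arm, the plain Poisson SE of the log IRR is √(2/(nμ)), and the SE under overdispersion is √(2(1/μ + k)/n). For μ = 2, k = 1 these are √(2/48) = 0.204 and √(3/24) = 0.354, a ratio of 1.73. The planned model is not a plain Poisson, however. Arm is constant within site, so the site intercept absorbs part of the excess variation.

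Simulated results for the mixed Poisson model (6 × 8 participants, true IRR 1, no covariate, t(4) standing in for Satterthwaite):

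| μ | k | Site SD | Var/mean within site | Mean SE / empirical SD | Coverage, normal | Coverage, t(4) |
|---|---|---|---|---|---|---|
| 1 | 1 | 0 | 2 | 0.367 / 0.439 | 87.5% | 97.3% |
| 2 | 1 | 0 | 3 | 0.291 / 0.372 | 85.8% | 94.7% |
| 2 | 1 | 0.2 | 3 | 0.321 / 0.385 | 86.7% | 95.7% |
| 4 | 1 | 0 | 5 | 0.258 / 0.339 | 82.7% | 92.9% |
| 4 | 2 | 0 | 9 | 0.358 / 0.462 | 82.3% | 93.0% |

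Over all overdispersed settings tried (k 0.5–2; means 1–4 with site SD 0, means 1–2 with site SD 0.2), the SE was about 8–24% too small. Coverage was 82–93% with normal limits and 93–99% with t(4). A plain Poisson model would have given 49–91%.

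One separate run with variance nine times the mean gave lower coverage, 69% (normal) and 84% (t(4)). Repeating that setting with 600 runs gave 82% and 92%, in line with the table, so I give the lower pair little weight.

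**Step 3, the alternative.** A mixed negative binomial model at μ = 2, k = 1, site SD 0.2 gave a mean SE of 0.379 against an empirical SD of 0.403. Coverage was 92.0% (normal) and 97.8% (t(4)).

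**The case against.** The best defence is that the SAP is silent on exposure and does not exclude it. SAP 5.1 imports the protocol's definitions, that definition is a rate, and Table 16 reports an IRR. A careful analyst would add the offset. That stands in part. But the model sentence speaks of counts and Table 16 has no person-time, so a literal reading gives a ratio of mean counts.

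A reader might go further than the documents allow in four ways:

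- **That diaries are shorter in the intervention arm, so the ratio favours it.** Both arms have a nominal six-month diary, its start is not defined, and the direction reverses under SAP 2.7. The SAP also refers to protocol version 5.0, while the protocol reviewed is version 3.0, so the timing text may since have changed.
- **That the null ratio could be 24/28 = 0.86, because the last booster is at week 24.** The sentence in protocol 10.1 concerns the return of diaries, not when recording stops, and Table 3 marks the diary to week 28.
- **That the interval is too narrow.** SAP 5.2 applies the Satterthwaite correction to the Poisson model too, and with about 4 degrees of freedom coverage is near nominal. In the worked case the mixed Poisson interval (95.7%) is closer to 95% than the negative binomial one (97.8%). The shortfall appears only if the correction is not achieved for the count model, and the SAP does not say how it would be.
- **That a false between-site variance is handed to the main trial.** The SAP plans no site variance or ICC for falls.

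It is also fair to say that prior falls are a natural baseline value. The SAP merely fails to name them.

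**Conclusion.** The point holds as a gap in specification. The protocol promises a rate, while the model and table as written deliver counts. Observation time will vary between participants, and may vary by arm in a direction on which the documents disagree. From planned timing alone the null ratio lies between about 0.93 and 1.08, and is 1.00 if diary time is equal. The standard error is about 8–24% too small under the assumed dispersion. Whether that affects the interval depends on whether the small-sample correction is really applied.

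The dispersion values, fall rates, equal cluster sizes and t(4) are assumptions, not figures from the documents. The impact is modest: the comparison is ancillary, no p-values are reported, and falls are not a progression criterion. The fix is nearly free, so it is worth making before analysis.

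**What to change.** - **SAP 5.2:** fit a mixed negative binomial model (or a Poisson model with a participant-level random effect as well as the site effect), with log(diary days observed) as offset. Name falls in the last six months as the baseline covariate. State how the small-sample degrees of freedom are obtained for the count model.
- **Diary window:** define the same diary start and end in both arms, and include part-diaries through the days they cover. Say whether the 90% completion rule in SAP 5.4 applies to the diary.
- **SAP Table 16:** report falls, person-years and the rate per person-year by arm with the IRR. Add the proportion who fall at least once and the injury and fracture rates from protocol 7.8.
- **Timing:** reconcile protocol 7.7 with SAP 2.7.

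The cost is SAP wording, one derived variable (diary days) and possibly a slightly wider interval.
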